### **E.2.2 12-lead ECG**

The following variables will be summarized at the Baseline Visit:

- Heart rate
- PR interval
- QT interval
- QRS interval
- QTc (corrected)
- Overall result

A summary of each electrocardiography (ECG) parameter will be provided by treatment group. In addition, a by-subject listing of 12-lead ECG results will be provided.

**APPENDIX F. ADVERSE EVENTS OF SPECIAL INTEREST****F.1. Potential Risks**

The following potential risk factors will be presented as adverse events of special interest (AESI):

- Hypersensitivity: Hypersensitivity Standardised MedDRA Query (SMQ) Narrow
- Hyperkalemia: Hyperkaliemia MedDRA PT, Blood potassium abnormal MedDRA PT, Blood potassium increased MedDRA PT
- Hypertension: Hypertension MedDRA SMQ Narrow

**F.2. Events of Special Interest**

The following will be presented as AESI:

- Hepatotoxicity: Drug related hepatic disorders Comprehensive SMQ broad
- Pulmonary Hypertension: Pulmonary Hypertension SMQ narrow
- Cardiac Valve disorders: Cardiac Valve disorders high-level group term (HLGT)
- Adrenal disorder: high-level term (HLT) Adrenal gland disorders not elsewhere classified (NEC), HLT Adrenal cortex tests

**F.3. Events Under Monitoring**

The following will be presented as AESI:

- Malignancies: Malignancies MedDRA SMQ Narrow
- Congestive heart failure: Cardiac failure MedDRA SMQ Narrow
- Retinal effects due to Vascular Endothelial Growth Factor (VEGF) expression: Retinal disorders SMQ Narrow

## ABBREVIATIONS

| Abbreviation | Definition                     |
|---------------------|---------------------------------------|
| CEC                 | Clinical Endpoint Committee           |
| CHF                 | congestive heart failure              |
| CKD                 | chronic kidney disease                |
| CRP                 | C-reactive protein                    |
| CV                  | cardiovascular                        |
| DD                  | dialysis-dependent                    |
| DVT                 | deep vein thrombosis                  |
| EAS                 | Endpoint Adjudication System          |
| EOT                 | end of treatment                      |
| ESA                 | erythropoietin-stimulating agent      |
| EU                  | European Union                        |
| GSCD                | global study completion date          |
| HF                  | heart failure                         |
| HR                  | hazard ratio                          |
| IDMC                | Independent Data Monitoring Committee |
| MACE                | major adverse cardiovascular events   |
| MAR                 | missing at random                     |
| MI                  | myocardial infarction                 |
| MNAR                | missing not at random                 |
| NDD                 | non-dialysis dependent                |
| NI                  | noninferiority                        |
| PE                  | pulmonary embolism                    |
| RMST                | restricted mean survival time         |
| ROW                 | rest of world                         |
| SAP                 | statistical analysis plan             |
| SMQ                 | Standard MedDRA Queries               |
| uACR                | urine albumin creatinine ratio        |
| US                  | United States                         |

## 1 INTRODUCTION

This statistical analysis plan (SAP) describes the methods to be used to analyze the major adverse cardiovascular events (MACE) in Akebia's PRO2TECT Protocols (AKB-6548-CI-0014 and AKB-6548-CI-0015) and INNO2VATE Protocols (AKB-6548-CI-0016 and AKB-6548-CI-0017). CI-0014 and CI-0015 are studying vadadustat in subjects with non-dialysis dependent (NDD) chronic kidney disease (CKD) while CI-0016 and CI-0017 are studying vadadustat in dialysis-dependent (DD) CKD. These four trials, referred to hereafter as CI-0014, CI-0015, CI-0016, and CI-0017, constitute Akebia's Phase 3 program for vadadustat.

Note that while this SAP covers all four trials, the analyses will be performed by study pair, PRO2TECT (CI-0014 and CI-0015) or INNO2VATE (CI-0016 and CI-0017), in particular at such time as the specified target is met in each respective pair, independent of the progress in the other pair of studies. Thus, the analyses in this SAP will not necessarily be conducted on the same calendar date.

In addition to the plans for analysis of MACE, this SAP also describes plans for analysis of other cardiovascular and thrombotic events.

(For simplicity, sometimes MACE refers to the singular and sometimes the plural. The context is always clear.)

Protocol CI-0014 is a "correction study". CI-0014 enrolls subjects not on an erythropoietin-stimulating agent (ESA).

Protocols CI-0015 and CI-0017, the "conversion studies", which are designated here as CI-0015/17, enroll subjects on any dose of ESA.

Protocol CI-0016 is a "correction/conversion study", enrolling incident dialysis subjects who may be on an ESA or not.

For each safety parameter described in this SAP, the outcomes of most interest are estimates that combine data from each pair CI-0014/15 and CI-0016/17 calculated by considering as a stratum each component study of the pair. In addition, estimates will be presented for each study separately.

The protocols for the four studies, as well as the general SAPs for the PRO2TECT and INNO2VATE Protocols, provide information about the plans for the studies and their analyses exclusive of the MACE analyses.

This SAP contains language and programming code that specifies the intent of each analysis. The sponsor will finalize and sign this document prior to locking the database and unblinding. Many of the analyses described in this SAP are quite complex. A blinded team of clinicians and statisticians will review the data carefully to develop conventions and analytic methods not anticipated in writing this SAP.

## 2 STUDY DESCRIPTION

CI-0014 and CI-0015 are studying vadadustat in subjects with NDD-CKD while CI-0016 and CI-0017 are studying vadadustat in DD-CKD. Darbepoetin alfa is the control drug in all four studies.

The Phase 3 program is designed so that meta-analyses of the PRO2TECT and INNO2VATE pairs of studies will have a sufficient number of independently adjudicated endpoints to allow a meaningful comparison of vadadustat and darbepoetin alfa with respect to MACE in each pair of trials. The PRO2TECT pair of trials will continue until at least 631 subjects experience an adjudicated MACE in the pair of trials. Similarly, the INNO2VATE pair of trials will continue until at least 631 subjects experience an adjudicated MACE in that pair. The individual trials in each pair will continue after the planned number of MACE have occurred in order to ensure that each subject is followed the minimum amount of time specified in the individual protocols.

### 2.1 Study Periods

#### 2.1.1 The Correction (CI-0014) and Correction/Conversion Study (CI-0016)

Following randomization, CI-0014 and CI-0016 will have five periods:

- Correction
  - CI-0014: Correction Period (Weeks 0-23): initial period on study medication for correction of Hb
  - CI-0016: Correction and Conversion Period (Weeks 0-23): initial period on study medication for correction of Hb or conversion to study treatment
- Maintenance Period (Weeks 24-52): this period will be divided into weeks 24-36 (primary efficacy evaluation period) and Weeks 40-52 (secondary efficacy evaluation period)
- Long-Term Treatment Period (Weeks 53-End of Treatment [EOT]): continued study medication to assess long-term safety
- Follow-Up (EOT + 4 weeks): post-treatment visit (either in person or by telephone) for safety
- Continued MACE Follow-up: each subject, except those who are lost to follow-up or who withdraw consent, will be followed for MACE until the end of the study.

### 2.1.2 The Conversion Studies (CI-0015 and CI-0017)

Following randomization, each conversion study will have four periods:

- Conversion and Maintenance Period (Weeks 0-52): conversion to study medication for maintaining Hb (Weeks 0-23), primary efficacy evaluation (Weeks 24-36), and secondary efficacy evaluation (Weeks 40-52)
- Long-term Treatment Period (Week 53-EOT): continued study medication to assess long-term safety
- Follow-up Period (EOT + 4 weeks): post-treatment visit (either in person or by telephone) for safety
- Continued MACE Follow-up: each subject, except those who are lost to follow-up or who withdraw consent, will be followed for MACE until the end of the study.

Each pair of trials (CI-0014/15 and CI-0016/17) will continue until at least 631 events occur in the respective pair.

## 2.2 Method of Assigning Subjects to Treatment Groups

Subjects will be randomized 1:1 using permuted block randomization. Randomization will be stratified in each of the four studies by the following:

- Geographic region
  - United States (US)
  - European Union (EU)
  - Rest of World (ROW)
- New York Heart Association congestive heart failure (CHF) class
  - Class 0 or I
  - Class II or III
- Baseline Hb (g/dL)
  - <9.5 versus  $\geq$ 9.5 for CI-0014 and 0016
  - <10 versus  $\geq$ 10 for CI-0015 and 0017

## 2.3 Primary Safety Outcome: Major Adverse Cardiovascular Event (MACE)

The primary safety outcome in each study is MACE, defined as all-cause mortality, nonfatal myocardial infarction (MI), or nonfatal stroke, occurring at any time on or following first dose date and prior to each subject's end of study (EOS) date.

## 2.4 Blinding

All four studies are randomized open-label trials. An interactive web response system governs treatment assignment. Investigators are not aware of which treatment will be assigned next.

The studies involve blinded adjudication of MACE, the use of an unblinded independent data monitoring committee (IDMC), and an identical schedule of visits, procedures, and assessments for both treatment groups in order to reduce the potential for bias.

The protocols discuss the method of guiding dose adjustment for vadadustat and darbepoetin alfa.

As further mechanisms to reduce potential execution bias in the trials, special steps have been taken to restrict access to the study data (see the Blinding Procedures and Oversight Plan).

## 2.5 Sample Size

The primary safety endpoint is the time from first dose date to the first adjudicated MACE. This section describes the justification for the sample sizes of the four studies.

### 2.5.1 The PRO2TECT studies (CI-0014 and CI-0015)

The primary safety analysis will be based upon all first events that accrue over the two PRO2TECT trials. If the noninferiority (NI) margin is 1.25 and the event rate is the same in the two treatment groups (i.e., the hazard ratio (HR) is 1.0), then 631 events are needed to establish NI with 80% power; 631 events yields more than 90% power to exclude an NI margin of 1.30. If the HR is 0.95 favoring vadadustat, the power is above 90% when the NI margin is 1.25.

Justification for the NI margin of 1.25 for FDA decision making and 1.30 for EMA decision making is provided in [Appendix C](#).

An annual MACE rate of 10% is anticipated. This rate is based on a comprehensive review of available epidemiology and prospective clinical studies in NDD-CKD. Therefore, a projected total of 3700 subjects will be enrolled in studies CI-0014 and CI-0015. With 1850 subjects planned per treatment group in studies CI-0014 and CI-0015 and a planned accrual period of approximately 20 months, and up to 36 months of follow-up (with expected mean follow-up about 2 years), the number of MACE in each study will be a function of the actual pattern and size of enrollment as well as the duration of follow-up.

### 2.5.2 The INNO2VATE studies (CI-0016 and CI-0017)

The primary safety analysis will be based upon all first events that accrue over two INNO2VATE studies (CI-0016 and CI-0017). As described in the previous section, to have 80% power to establish NI if the NI margin is 1.25 and the event rate is the same in the two treatment groups (i.e., the HR=1.0), 631 events are needed; this number of events yields more than 90%

power to exclude an NI margin of 1.30. If the HR is 0.95 favoring vadadustat, the power is above 90% when the NI margin is 1.25.

An annual MACE rate of 12% is anticipated. This rate is based on a comprehensive review of available epidemiology and prospective clinical studies in DD-CKD. Therefore, an estimated total of 3700 subjects will be enrolled in studies CI-0016 and CI-0017. With 1850 subjects planned per treatment group enrolled in study CI-0016 and CI-0017, a planned accrual period of approximately 20 months, and up to 36 months of follow-up (with expected mean follow-up about 2 years), the number of MACE in each study will be a function of the actual pattern and size of enrollment as well as the duration of follow-up.

### **3 SAFETY OUTCOMES**

This section defines the outcomes to be used for the analyses of MACE and related events.

#### **3.1 Adjudicated Outcomes**

Study investigators will solicit potential cardiovascular events at each study visit. Each of these potential events will be recorded on the eCRF. Potential cardiovascular events will also be identified through periodic review of Standard MedDRA Queries (SMQs) of adverse events and serious adverse events irrespective of the source of identification. An Endpoint Management Plan will provide details describing the SMQs terms and processes related to identifying these potential events. Events not reported by study investigators identified through SMQ search or CEC will be manually entered into EAS (Endpoint Adjudication System) database.

The Clinical Endpoint Committee (CEC) adjudicates all potential cardiovascular events. The formal cardiovascular safety analyses will only include CEC-adjudicated events (i.e., events confirmed by the CEC).

The CEC adjudicates the following events CEC Manual of Operations (MOP) outlines the program endpoint definitions and requirements for committee adjudication.

- All-cause mortality (The CEC will attribute cause of death to responsible underlying disease cause).
- Non-cardiovascular death
- Unknown death
- Cardiovascular death
  - Sudden death
  - Non-sudden cardiovascular death

- Fatal or nonfatal MI
- Fatal or nonfatal stroke
- Thromboembolic event
  - Arterial thrombosis
  - Deep vein thrombosis (DVT)
  - Pulmonary embolism (PE)
  - Vascular access thrombosis
- Hospitalization for heart failure (HF)

### **3.2 Time to Adjudicated MACE: Primary Safety Outcome**

An adjudicated MACE, the primary safety outcome, is defined as any death, CEC-confirmed nonfatal MI, or CEC-confirmed nonfatal stroke occurring between first dose date and each subject's EOS date. The following subsections describe variations on, and components of, the primary safety outcome.

#### **3.2.1 Potential MACE: Descriptive Safety Outcome**

All potential MACE are all cases adjudicated as MACE by the CEC (i.e., primary safety outcome events confirmed by the CEC) plus those potential MACE cases reported by the investigator, submitted for adjudication, but then adjudicated as non-MACE (i.e., events refuted by the CEC). All deaths are included in this descriptive safety outcome.

#### **3.2.2 Time to MACE Within 4 Weeks of End of Treatment**

Only a MACE that occurs up to and within 28 days inclusive after permanent discontinuation of study treatment (End of Treatment, EOT) will be included as a MACE Within 4 weeks of End of Treatment.

#### **3.2.3 Individual CEC-Adjudicated Components of MACE: Descriptive Safety Outcome**

The components of CEC-Adjudicated MACE are as follows:

- All-cause mortality
- CEC-confirmed nonfatal MI
- CEC-confirmed nonfatal stroke

The total number of these outcomes equals the total number of CEC-adjudicated MACE. They will be reported simply to help interpret the primary MACE outcome. No formal analysis of these outcomes is planned.

### **3.2.4 Time to Components of Adjudicated MACE**

The following CEC-confirmed MACE will be reported and analyzed as time-to-first event. As with the primary safety outcome, the CEC adjudication of cause does not exclude any death from all-cause mortality.:

- All-cause mortality: death from cardiovascular (CV), non-CV, and unknown causes.
- Cardiovascular death
  - Fatal MI
  - Fatal stroke
  - Sudden death
- Non-cardiovascular death
- Non-fatal MI
- Non-fatal stroke

### **3.3 Time to Expanded MACE**

The studies have several outcomes that expand the definition of MACE. Each of these outcomes includes MACE (all-cause mortality, nonfatal MI and nonfatal stroke) plus one or more other type of event. The events are as follows:

- MACE plus thromboembolic event
- MACE plus thromboembolic event excluding vascular access thrombosis
- MACE plus hospitalization for heart failure (HF)
- MACE plus hospitalization for HF or thromboembolic event
- MACE plus hospitalization for HF or thromboembolic event excluding vascular access thrombosis

### **3.4 Time to cardiovascular death, nonfatal MI, or nonfatal stroke**

This alternate MACE definition is the same as the primary safety outcome, except includes only deaths positively adjudicated by the CEC as cardiovascular (i.e., only CEC-confirmed CV deaths). This excludes non-cardiovascular deaths as well as unknown deaths.

## **4 STATISTICAL ANALYSIS**

For each subject in the four studies, duration of follow-up will be calculated as the number of days between date of first dose date and last contact date during the study plus one. For each outcome, the number of events that occur during that period may be included in the analysis. The event rate will be calculated as the number events divided by the duration of at-risk follow-up in

person-years. Survival analyses will include only the first event for each subject in that period. For each type of event, the event rate will be summarized by treatment group for each study and for each pair of studies (CI-0014/15 and CI-0016/17).

For each type of event that includes all-cause death (including the primary endpoint), the method of analysis for each pair of studies will be a Cox regression with the randomized treatment assignment as a predictor. The models will be stratified by study. Subjects without an event will be censored at their last study contact (visit or telephone contact) at which all components of the outcome were assessed. Deaths that occur between withdrawal of consent or loss to follow up and the global study completion date (GSCD) and that are identified, prior to database lock, through public records will be included in the analyses as an event. The models will use other covariates as well, as described below.

For all other events, analyses will use competing risk methods. These methods produce valid estimates of the marginal probability of the event in case other events preclude observation of the event of interest. For each pair of studies, the models include the randomized treatment assignment as a predictor and, should a competing event not occur, subjects will be censored on their last study contact (visit or telephone contact) at which all components of the outcome were assessed. The models will use other covariates as well, as described below. Models for the overall analysis of PRO2TECT and of INNO2VATE will also stratify by study. [Appendix A](#) provides SAS code for the competing risk analysis.

The studies will enroll subjects from many centers; however, most centers will have small sample sizes. Therefore, as described in the general SAPs for PRO2TECT and INNO2VATE, no center-specific analyses are planned.

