9.3.12 End of Study Subject Status

The End of Study (EOS) assessment documents the subject status at the global study completion or at the time of subject withdrawal of consent or when subject is deemed LTFU or upon death. The table below outlines how to handle each subject based on their status.

The following activities/procedures will be performed. At minimum,

- EOS subject status

Subject Status	Global Study Completion
Subject on Study Medication (includes those on temporary interruption) at time of global study completion	
● Perform EOT visit● Perform the Follow-up visit 4 weeks after EOT and include EOS subject status

Subject permanently discontinued study medication and continues to be followed in the study	Optimal data collection would include the following assessments: 
 • EOS subject status (must collect at minimum) • MACE Endpoint Questionnaire • AE Assessment NOTE: EOT and the Follow-up visit 4 weeks after EOT visit to be performed at time study medication is permanently discontinued.
Subject Lost to Follow-up	Work with third party vendor to ascertain vital status and complete EOS subject status. If subject-site contact is reestablished and possible, collect available information for EOS subject status.
Subject Withdrawn Consent	Complete the EOS subject status form at the time of withdrawal of consent, absolute refusal of ALL methods of MACE and health status follow-up.
Subject Death	Complete the EOS subject status form at the time of death (see Section 10 Adverse Events for more details on other actions related to reporting a death).

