### *Study CI-0015*

- Conversion and Maintenance Period (Weeks 0-52):
  - Weeks 0 to 23: conversion to study treatment for maintaining Hb
  - Weeks 24 to 36: PEP
  - Weeks 40 to 52: SEP

After Week 52, subjects in both studies will proceed to the following 2 periods:

- **Long-Term Treatment Period (Weeks 53-End of Treatment [EOT]):** continued treatment with study medication to assess long-term safety
- **Follow-up Period (EOT + 4 weeks):** post-treatment visit (either in person or by telephone) to assess safety

The duration of the trial will depend on how long it takes for a total of 631 adjudicated MACE to occur in the 2 studies combined. A separate SAP will describe the planned MACE analyses, including the method planned for pooling data from the 2 PRO2TECT studies.

The safety reporting period for a subject enrolled in this study begins upon randomization and ends at the final protocol-required study contact (visit or telephone), also known as a subject's end of study (EOS). In addition, the Investigator should report any adverse event (AE) that occurs after this period if he or she assesses it as possibly or probably related to the study medication.

According to the schedule of visits in the protocol, no laboratory assessments, physical exams, or other procedures are planned after the subject's permanent discontinuation of study medication, also known as EOT; however, AE and rescue therapy assessments, including monitoring for MACE endpoints, will continue until a subject's EOS.

The analysis time periods for efficacy divide the Correction/Conversion and Maintenance periods, Year 1 collectively, into four windows (see [Table 1](#)).

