#### **4.2 Global Study Completion Date**

The sponsor will notify the sites approximately three months prior to the global study completion date (GSCD) for each study so that they can schedule visits with all subjects who are alive and have not withdrawn consent. At that visit the investigators should try to assess whether the subjects have had any MACE, Hospitalized for HF or Thromboembolic event. At a minimum the investigators will attempt to contact each subject to determine whether that subject is still alive. Additionally, investigators will request that subjects who continued study treatment until this visit come in for another follow-up visit four weeks later.

Operationally this plan is designed to capture all MACE, hospitalized for HF and Thromboembolic events that occurred in subjects still being followed and with onset within three

months of GSCD in the clinical database. Should subjects who remained on study treatment until that visit subsequently experience MACE, Thromboembolic events or hospitalized for HF between that visit and four weeks later, these events may also be captured.

Analytically, any outcome event with onset on or before the last contact date will be included in the primary safety outcome analysis, and all subjects without events will be censored at the last contact date.

The earliest GSCD of a pair of studies will be a date that ensures each pair of studies will have the planned number of safety outcome events (i.e., 631) and each study in each pair has the protocol-required amount of safety follow-up.

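### MACE SAP Section 4 counts deaths found in public records after withdrawal or loss but leaves survivors found by the same search censored at loss; Section 4.2 gives a different censoring date, and Sections 3.2 and 4.2 different event windows

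*SAP*

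**What the plan says.** **Which deaths count.** MACE SAP Section 4 counts as events, if found in public records before database lock, "Deaths that occur between withdrawal of consent or loss to follow up and the global study completion date (GSCD"). This applies to every outcome that contains all-cause death, including the primary.

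**Who is censored, and when.** The preceding sentence reads: "Subjects without an event will be censored at their last study contact (visit or telephone contact) at which all components of the outcome were assessed". Section 4.4 repeats that date for MACE. Section 4.6 censors all-cause death at last contact. No text moves the date for a subject whom the search finds alive.

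**The search finds both.** Protocol 7.5.5.5 (Amendment 7-COL) seeks alive-or-deceased status at study completion for all randomized subjects, including those lost. Section 7.5.2 assigns a vendor to trace lost subjects.

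**Other windows and dates in the MACE SAP.**
- Section 4, opening paragraph, sets the period from first dose to last contact: "Survival analyses will include only the first event for each subject in that period".
- Section 3.2 ends the MACE window at EOS: "CEC-confirmed nonfatal stroke occurring between first dose date and each subject's EOS date".
- Section 4.2 ends its event window at the date of last contact, whatever was assessed then. Its censoring rule is equally general: "all subjects without events will be censored at the last contact date".
- Section 4.3 defines last contact as any site contact, separately from the last visit at which all events could be assessed.

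**EOS.** The general SAP, Section 2.2, says the safety period "ends at the final protocol-required study contact (visit or telephone), also known as a subject's end of study (EOS"). Protocol 9.3.12 records EOS status at study completion or "at the time of subject withdrawal of consent or when subject is deemed LTFU or upon death".

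**The concern.** Follow-up after loss depends on the outcome: a subject who dies contributes both the death and the time up to it, while one known to be alive contributes nothing after the last full assessment. If the arms lose subjects at different rates, the arm with more loss gains more of these one-sided events, even when loss has nothing to do with risk. The trial is open-label, so unequal withdrawal is plausible.

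The affected quantity is the hazard ratio tested against 1.25 and 1.30. More loss on vadadustat costs power; more loss on darbepoetin raises the chance of wrongly declaring noninferiority. All-cause death is the clearest case, because vital status is all that endpoint needs.

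Separately, two programmers working from Sections 4 and 4.2 could use different censoring dates for the same subject.

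**Working it through.** **1. The rules side by side (MACE SAP).**

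| Section | Event window ends | Event-free subject censored at |
|---|---|---|
| 3.2 | EOS date | not stated |
| 4, opening paragraph | last contact | not stated |
| 4, Cox paragraph | GSCD, for record deaths | last contact with all components assessed |
| 4.2 | last contact | last contact (any, by 4.3) |
| 4.4 | not stated | last contact with all components assessed |
| 4.6, all-cause death | not stated | last contact |

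A registry search is not site contact with the subject, so a traced survivor stays at loss under every row. A record death after loss is inside the Section 4 Cox rule but outside Section 4.2. For a subject who withdrew consent it is also outside Section 3.2, because Protocol 9.3.12 completes the EOS form at withdrawal. For lost subjects EOS is ambiguous: the table there has EOS status completed with the vendor's help at study completion.

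**2. The plan's own figure.** Events = 4(1.960 + 0.842)² / (ln 1.25)² = 631, as stated in Section 2.5.1, with 80% power. That calculation is sound; the issue is censoring.

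**3. Size of the shift.** Cox simulation, 1,850 per arm, true HR 1. From the plan: sample size, 20-month accrual, about 10% annual MACE. Assumed: death hazard 0.065 and nonfatal MI/stroke hazard 0.04 per year (deaths 0.065/0.105 = 62% of MACE); follow-up uniform from 1.0 to 2.67 years; exponential loss unrelated to risk; complete records.

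| Annual loss, vadadustat vs darbepoetin | MACE HR, Section 4 rule | MACE HR, record deaths omitted | All-cause death HR |
|---|---|---|---|
| equal, 5% | below 0.1% | within 0.1% | no shift |
| 2 vs 1% | +0.6% | within 0.1% | +0.9% |
| 5 vs 2% | +1.7% | within 0.1% | +2.8% |
| 8 vs 3% | +2.9% | within 0.1% | +4.6% |

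The record deaths involved number about 6, 13 and 20 in the three unequal cases, on top of 613 to 635 first events. The MACE shifts vary with the inputs:
- 50% record capture: +0.3%, +0.9%, +1.4%.
- Follow-up of 1.33 to 3.0 years: +0.6%, +1.9%, +3.3%.
- Death share 48% to 76%: +0.4 to +0.7%, +1.4 to +2.1%, +2.3 to +3.5%.

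For all-cause death, censoring confirmed-alive subjects at their vital-status date returns the shift to 0.0%. This requires deaths and survivors to be traced equally well, and either complete tracing or loss unrelated to risk.

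**4. A second calculation with other inputs.** With 70% of MACE fatal and loss of 6 vs 3% per year, event rates per person-year under Section 4 are 0.1100 and 0.1076, ratio 1.022. Without record deaths they are 0.1056 and 0.1056, ratio 1.000.

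**5. Consequence at margin 1.25.** SE(log HR) = 2/√631 = 0.0796. For a shift factor h:
- Power at true HR 1 = Φ(ln(1.25/h)/0.0796 − 1.96). For h = 1.006, 1.017, 1.029 this gives 78%, 74%, 69%.
- If darbepoetin loses more by the same amounts, one-sided error at true HR 1.25 = Φ(ln h/0.0796 − 1.96), giving 3.0%, 4.0%, 5.5% against a nominal 2.5%.

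**The case against.** **The specific sentence governs.** Section 4's rule on record deaths is explicit and can be read as overriding the general windows. That settles which deaths count. It does not settle the censoring date or deal with traced survivors.

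**Unequal loss is assumed.** The documents give no loss rates and no reason to expect one arm to lose more. Protocol 7.5.5.3 to 7.5.5.5 work against loss: withdrawal means refusing every form of follow-up, reduced contact is offered, and tracing is extensive. At 2 vs 1% per year, power moves only from 80% to 78%. The largest figures need 8 vs 3% and complete records. This stands, and it limits the severity. More vadadustat loss is also the conservative direction for a safety claim, though the reverse is not.

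**An on-treatment analysis exists.** The analysis of MACE within 28 days of end of treatment (Section 3.2.2) removes most late post-loss deaths. It is only a partial check, since it also removes later off-treatment events. Protocol 11.7.1 points to the MACE SAP for sensitivity analyses, but none there isolates post-loss deaths.

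**Stronger readings the documents do not support.**
- A reader might infer that every added death lies outside the Section 3.2 window. That is clear only for withdrawn consent.
- A reader might infer that the Section 4.2 dates bias the HR by a definite amount in the other direction. That depends on how many lost subjects are re-contacted. If the contact assesses all components, Sections 4 and 4.4 censor there too.
- A reader might expect the Section 4 result and the two sensitivity analyses to bracket the true HR. They need not. With equal 5% loss that is risk-related on vadadustat only, the Section 4 rule, omission of record deaths, and carrying survivors forward gave −0.7%, −1.3% and −0.4%. With fivefold risk-related loss in both arms (5 vs 2% per year) and 50% capture they gave −0.5%, −1.9% and −1.7%.

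**Conclusion.** The concern holds in this form: deaths after withdrawal or loss enter, traced survivors' time does not, and the MACE SAP states conflicting event windows and censoring dates. The conflict and the asymmetry are matters of text and need no assumption.

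The effect on the hazard ratio is conditional. There is none if loss is equal and unrelated to risk. It is about +0.5% to +3% for MACE and +1% to +5% for all-cause death across the assumed range with complete records, and about half that for MACE at 50% capture. The documents do not show that the primary result will be biased, or in which direction. With planned power of 80%, a shift of 1 to 2% is still worth guarding against. This should be corrected before lock; it does not undermine the design or the 631-event target.

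**What to change.** 1. **One rule for primary MACE** in Sections 3.2, 4, 4.2 and 4.4. Censor event-free subjects at the last contact with all components assessed. State whether post-loss record deaths are in the primary. Protocol 11.5, which uses all MACE data regardless of discontinuation, supports keeping them; if they stay, extend the death window to the GSCD.
2. **All-cause death (Section 4.6).** Count public-record deaths and censor subjects confirmed alive by the same search at their vital-status date.
3. **Sensitivity analysis.** Prespecify primary MACE without post-loss record deaths. Optionally add one that carries confirmed-alive subjects to their vital-status date, noting that nonfatal events after loss go unseen there. Report loss and completeness of tracing by arm alongside.

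The cost is wording, one derived date and one or two extra analyses. No death has to leave the primary, so its conditional shift remains and the sensitivity analysis is there to expose it. No rule is unbiased under every pattern of loss or tracing, and item 2 works only if deaths and survivors are traced equally well.
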